7.14 Adverse Events Assessments

7.14.1 Definitions of Adverse Events and Serious Adverse Events

7.14.1.1 Adverse Events

An adverse event is any noxious, pathologic, or unintended change in anatomical, physiologic, or metabolic function as indicated by physical signs, symptoms, or laboratory changes occurring in any phase of a clinical study, whether or not considered investigational product-related. This includes an exacerbation of a pre-existing condition.

Adverse events include:

- Worsening (change in nature, severity, or frequency) of conditions present at the onset of the study
- Intercurrent illnesses
- Drug interactions
- Events related to or possibly related to concomitant medications
- Clinically significant abnormal laboratory values (includes shifts from baseline within the range of normal that the Investigator considers to be clinically important)
- Clinically significant abnormalities in physical and neurological examination, vital signs, ECG

Throughout the study, the Investigator must record all adverse events on the AE CRF, regardless of the severity or relationship to investigational product. The Investigator should treat patients with adverse events appropriately and observe them at suitable intervals until the events stabilize or resolve. Adverse events may be discovered through observation or examination of the patient, questioning of the patient or his parent(s)/legally authorized guardian(s), complaint by the patient or his parent(s)/legally authorized guardian(s), or by abnormal clinical laboratory values or physical findings.

In addition, adverse events may also include laboratory values that become significantly out of range. In the event of an out-of-range value, the laboratory test should be repeated until it returns to normal or can be explained and the patient's safety is not at risk.

Additional illnesses present at the time when informed consent is given are regarded as concomitant illnesses and will be documented on the appropriate pages of the CRF. Illnesses first occurring or detected during the study, and worsening of a concomitant illness during the study, are to be regarded as adverse events and must be documented as such in the CRF.

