10.7.3 Clinical Laboratory Evaluations

Laboratory values (eg, chemistries, hematology, etc) including CSF components will be summarized in terms of the absolute value and change from baseline at each time point by treatment group. The number and percentage of patients with any clinically significant post-baseline laboratory result will be presented by treatment group.

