The AE categories 1-7 will be presented by each treatment group for patients in the Safety Population, while the AE categories 8-12 will be presented by each treatment group for patients in the Safety Population who received idursulfase-IT. IT administration process-related AEs will be summarized by IT administration method (LP or IDDD) as well. The AE categories 10-11 will be presented for patients in the Safety Population with the device implanted. The number and proportion of patients, and the number of corresponding AEs will be summarized in overall summary tables. In addition, the number and percentage of patients having any treatment-emergent AE within the AE categories 2, 5, 7-12 and the number of corresponding AEs will be displayed by MedDRA system organ class (SOC), preferred term (PT) and treatment group. The most common treatment-emergent AEs which happened in >10% patients in either treatment group will also be summarized by SOC and PT. The most common non-serious treatment-emergent AEs which happened in >5% patients in either treatment group will also be summarized by SOC and PT.

The number and percentage of patients having any treatment-emergent AE, and the number of corresponding AEs will be summarized by MedDRA SOC, PT and severity.

The number and percentage of patients having any treatment-emergent AE, and the number of corresponding AEs will be summarized by relationship to IV Elaprase, idursulfase-IT, and at least one IT treatment regimen, and summarized by MedDRA SOC and PT.

Furthermore, listings of all the AEs of categories 3-6 will be provided if applicable.

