6.8.2 Clinical and CSF Laboratory Evaluations

Chemistry and hematology serum laboratory and CSF (standard chemistries, glucose, protein, and cell counts) values will be summarized in terms of the absolute value and change from baseline at each scheduled study visit by treatment group. The total protein, glucose and total nucleated cells will be plotted for individual patients over time by scheduled study visit.

All the laboratory (chemistry, hematology, urinalysis and CSF) values will be categorized as a patient having had (1) a Clinically Significant (CS) value at any time during the study post baseline, and (2) no CS values at any time during the study post baseline. The number and percentage of patients in each category will be presented by treatment dose and overall. Patients with a Normal or non-CS value for a particular laboratory parameter at baseline who experience a change to CS for that laboratory parameter post-baseline will be identified and listed separately along with the corresponding laboratory values over time. The baseline is defined as the Screening measurement. If it is not available, the Pre-Surgery Day 1 of Week 1 measurement will be used as baseline.

If a particular laboratory measurement has been either repeated or retested, then the repeated or retested measurement for that laboratory parameter, with respect to date/time, will be used in the statistical analysis unless this value is invalid/missing. The handling of repeated or retested laboratory measurements should only consider the specific laboratory measurement that was repeated or retested.

6.8.3 12-Lead ECG Evaluations

The 12-lead ECG parameters (heart rate [bpm], PR interval [msec], QRS interval [msec], QT interval [msec] and the corrected QT interval (QTc) [msec]) will be summarized in terms of absolute value and change from baseline by visit and treatment group. The QTc interval will be calculated using Bazett's formula as QT divided by the square root of RR interval. The number and percentage of patients with ECG abnormalities post baseline will be presented by treatment group.

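### SAP 6.8.2 lets a retest replace a valid original laboratory result, which tends to remove transient abnormal values and, read literally, contradicts the clinically-significant-at-any-time table

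*SAP*

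**What the plan says.** The retest rule is in SAP 6.8.2. Its trigger is any repeat, whatever the reason: "the repeated or retested measurement for that laboratory parameter, with respect to date/time, will be used in the statistical analysis". The one exception is a repeat that is itself invalid or missing. The rule refers to the statistical analysis as a whole and exempts no table.

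The same section plans three kinds of output from these data:

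- by-visit summaries of value and change from baseline, with individual plots of total protein, glucose and total nucleated cells;
- a table classifying patients by whether they had "a Clinically Significant (CS) value at any time during the study post baseline";
- a listing in which patients who were normal or non-CS at baseline and "who experience a change to CS for that laboratory parameter post-baseline will be identified and listed separately".

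Baseline is the Screening value, or a pre-surgery value if Screening is unavailable.

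Two protocol sections bear on this. Section 10.7.3 plans the number and percentage of patients with "any clinically significant post-baseline laboratory result will be presented by treatment group" and has no replacement rule. Section 7.14.1.1 deals with results outside the reference range and says: "the laboratory test should be repeated until it returns to normal or can be explained and the patient's safety is not at risk".

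**The concern.** A retest rule is harmless if the reason for retesting is unrelated to the result, as with a haemolysed or lost sample. Here the protocol makes an abnormal result a reason to repeat and makes a normal result one of the reasons to stop. Replacing the original with the repeat then selects on the outcome. Values that were truly out of range but transient are the ones most likely to be overwritten.

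Two things are at stake. The by-visit laboratory and CSF displays could understate abnormality. In addition, two programmers working from the same data could produce different CS tables: one applies the retest rule throughout, the other counts every post-baseline value. The SAP does not say which is right.

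**Working it through.** The documents state no figure for this rule, so there is nothing to reproduce. The check is a comparison of the texts, followed by what arithmetic is possible.

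**1. Can a valid original be displaced?** Yes. The validity condition in SAP 6.8.2 applies to the repeat. No condition applies to the original.

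**2. Are repeats related to the result?** Under protocol 7.14.1.1, yes: an out-of-range value is the stated trigger. A repeat may still be abnormal, or worse, so the effect is a tendency rather than a certainty.

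**3. Does the rule conflict with the CS table?** Take a patient whose only CS value is at Week 16, with a valid repeat that is not CS.

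| Output | Retest rule applied literally | All valid values counted |
|---|---|---|
| Week 16 summary and plot | non-CS repeat | depends on the selection rule |
| CS at any time (SAP 6.8.2) | counted as never CS | counted as CS |
| Change-to-CS listing (SAP 6.8.2) | absent | present |
| Any CS result (protocol 10.7.3) | not counted | counted |

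The right-hand column is what the wording of the CS table and of protocol 10.7.3 describes. The middle column is what the retest rule describes. SAP 7.2, which lists changes from the protocol's analyses, does not mention the rule.

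**4. Size per displaced patient.** Planned arms are 32 IT and 16 control (SAP 4.1).

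- IT: 1/32 = 3.1 percentage points.
- Control: 1/16 = 6.25, about 6.3 percentage points.

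These apply only if the retest rule governs the CS table, and they use planned numbers, not the final Safety Population.

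**5. Total size.** This cannot be derived, because no retest rate or CS rate is given. Under the literal reading it is zero if no CS original is repeated or if every repeat is also CS, and it rises from there. The following is illustration only, and every rate and correlation in it is assumed.

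- *One visit.* Original and single repeat are bivariate normal with correlation 0.3 to 0.9, the out-of-range rate is 2.5% to 10%, and every abnormal original is repeated. P(repeat abnormal | original abnormal) = P(both abnormal) / P(original abnormal), which runs from about 10% to 69%. At a 5% rate and correlation 0.7 it is 39%, so the displayed abnormal rate falls from 5.0% to 2.0%.
- *Any time.* There are five post-baseline laboratory visits common to both arms (Weeks 4, 16, 28, 40, 52), treated as independent, with a CS probability q of 2% to 5% per visit. The share with any CS value is 1 − (1 − q)^5 = 9.6% to 22.6%. If half of the CS values persist on repeat, the table shows 1 − (1 − q/2)^5 = 4.9% to 11.9%. If all persist there is no change, and if none persist it shows 0%.

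The downward direction is built into this illustration, because only abnormal originals are repeated in it. The sizes carry no evidential weight.

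**6. Smaller gaps.** Protocol 7.14.1.1 foresees serial repeats, but the SAP's reference to date and time does not say which of several is used. The SAP also does not say whether a Screening repeat replaces the baseline value. These are missing details and the finding does not rest on them.

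**The case against.** The strongest reply is that the rule was meant only to choose one value per scheduled visit. The CS table refers to all laboratory values at any time, and that specific wording could be read as overriding a general sentence later in the section. On that reading only a scope statement is missing. The reading is possible, but the SAP does not state it. It would also leave the by-visit displays affected.

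A second reply is that the retest sentence does not cite protocol 7.14.1.1 and could mean a re-assay of the same sample, with later follow-up draws treated as unscheduled. The term is undefined, so this cannot be excluded. It is also not stated, and the rule covers repeats as well as retests.

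Third, the consequences are limited, and this stands. "Clinically significant abnormal laboratory values" are adverse events under protocol 7.14.1.1, and SAP 6.8.1 provides that adverse event counts "will be displayed by MedDRA system organ class (SOC), preferred term (PT) and treatment group". Safety analyses are descriptive, so neither type I error nor power is touched. The protection is partial, however. Adverse event tables do not show laboratory values, and adverse event listings cover only discontinuations, deaths, serious events and severe events. SAP 8.9 adds no further by-patient listing beyond those specified.

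Fourth, repeat CSF draws may be rare, since CSF is taken at fixed procedures. That is fair: the documents schedule no routine CSF repeats, and the CSF effect may be small.

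Finally, using the repeat in by-visit summaries can be called a convention. A convention tied to abnormal results still has a direction, and prespecifying it does not remove that.

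**Conclusion.** The concern holds. As written, SAP 6.8.2 replaces valid originals. Together with the protocol's instruction to repeat out-of-range tests, it will tend to take transient abnormal values out of the by-visit laboratory and CSF displays. Applied literally, it would code some patients as never having a CS value when they had one, against the SAP's own table and protocol 10.7.3.

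This should be corrected, but it does not threaten the trial's efficacy conclusions. The total effect is unknown and may be nil. The conclusion rests on two readings: that repeats in the SAP include those prompted under protocol 7.14.1.1, and, for the CS table, that the retest rule applies there.

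**What to change.** Amend SAP 6.8.2 as follows:

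1. A retest replaces the original only when the original is documented as technically invalid.
2. The CS-at-any-time table and the change-to-CS listing use every valid post-baseline value, whether original, repeat or unscheduled. This brings them into line with protocol 10.7.3.
3. One fixed rule, which does not depend on whether the result was abnormal, selects the valid value for by-visit summaries and for baseline. The original scheduled result is one example. The rule should also settle the case of several repeats.

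The cost is SAP wording and a selection flag in the laboratory dataset, using data already collected. Reported abnormality counts may be somewhat higher. The protocol's instruction on repeating tests is unaffected.

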7.11.10 Cerebrospinal Fluid Assessments

Cerebrospinal fluid samples will be collected via the IDDD or lumbar puncture and used to analyze standard safety laboratory parameters (chemistries, cell counts), albumin, GAG, and concentration of idursulfase enzyme. The CSF samples will also be analyzed for idursulfase-specific antibodies and antibodies with enzyme neutralizing activity (See Section 7.11.11).

Cerebrospinal fluid will be obtained from patients in the treated arm of the pivotal study and in the substudy at Screening (by lumbar puncture and under general anesthesia), during surgical implantation of the IDDD, prior to each intrathecal injection of investigational product, and at the EOS visit. Should the IDDD become clogged, undergo mechanical complications or otherwise not be accessible, the CSF sample may be obtained by lumbar puncture up to 12 times during the treatment phase of the study.

Patients in the no-treatment arm of the pivotal study will undergo lumbar puncture (under general anesthesia) to obtain CSF samples at the Screening and EOS Visits.

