8.3.1.1 Pre-surgery

- Physical and neurological examination*
- Height and weight*
- 12-lead ECG*
- Vital signs*
- Clinical laboratory tests (hematology, serum chemistry, urinalysis)*
- Coagulation tests ([PT, PTT] to be performed by the local laboratory)
- Concomitant medications, therapies/interventions, and medical/surgical procedures
- Adverse events

*The assessments indicated do not need to be repeated if completed as part of Screening assessments within 7 days prior to surgery.

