8.3.2.2 IT Injection

Patients will remain under observation in the hospital setting (eg, may include infusion center, post-anesthesia care unit [PACU; recovery suite], observation unit, short stay center) for 4 hours post IT injection for vital signs and other safety assessments. Thereafter, if deemed clinically stable by the Investigator, patients may leave the hospital setting (with exception of Visit Weeks 4, 24, and 48 at which serial blood sampling for PK evaluation is planned). The patient may need to be examined the following day (See Follow-up, Section 8.3.2.3) by the Investigator; however, there is no requirement for an overnight hospital stay. Note that, on IT Dosing Weeks, the IV infusion of Elaprase should be scheduled to occur a minimum of 48 hours after IT administration of idursulfase-IT.

- 12-lead ECG (performed within 4 hours of IT injection at Weeks 4, 16, 28, 40)
- Vital signs (collected at the following time points (± 10 minutes) in association with IT administration of idursulfase-IT: within 15 minutes prior to IT administration, 30 minutes post end of IT administration, 60 minutes post end of IT administration, 120 minutes post end of IT administration, and 4 hours post end of IT administration)
- CSF sample collection (performed at each IT Dosing Week prior to idursulfase-IT injection). Cerebrospinal fluid samples will be collected via the IDDD or lumbar puncture and used to analyze standard laboratory parameters (chemistries, cell counts), as well as GAG, concentration of idursulfase enzyme, albumin, and presence of idursulfase-specific antibodies. Analyses of CSF samples for antibodies and albumin will be performed at IT Dosing Weeks 4, 16, 28, and 40.
- idursulfase-IT injection
- Serum sampling for PK analysis (performed at Weeks 4, 24, and 48). Samples will be collected within 15 minutes (± 5 minutes) prior to intrathecal administration of idursulfase-IT and at 30 minutes (± 5 minutes), 60 minutes (± 5 minutes), 120 minutes (± 5 minutes), 4 hours (± 5 minutes), 6 hours (± 5 minutes), 8 hours (± 15 minutes), 12 hours (± 15 minutes), 24 hours (± 15 minutes), 30 hours (± 15 minutes), 36 hours (± 15 minutes) after the start of intrathecal administration.
- Concomitant medications, therapies/interventions, and medical/surgical procedures
- Adverse events

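### The any-post-baseline safety proportions in SAP 6.8.2 and 6.8.3 rest on unequal numbers of looks per arm (CSF 14 against 1; ECG about 9-10, possibly 17-18, against 5), so they are expected to run higher in the IT arm even with equal risk.

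*SAP*

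**What the plan says.** SAP 6.8.3 plans a patient-level ECG count: "The number and percentage of patients with ECG abnormalities post baseline will be presented by treatment group". SAP 6.8.2 sorts patients, for chemistry, hematology, urinalysis and CSF, by whether they had "a Clinically Significant (CS) value at any time during the study post baseline". Neither section limits the count to common visits or asks for the number of assessments behind it.

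The grouping of the laboratory table is not consistent. SAP 6.8.2 says "The number and percentage of patients in each category will be presented by treatment dose and overall", while protocol 10.7.3 says that "patients with any clinically significant post-baseline laboratory result will be presented by treatment group".

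The protocol schedules differ by arm:

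- **CSF.** Under protocol 7.11.10, IT patients are sampled at Screening, at implant surgery, before each injection and at end of study. Control patients "will undergo lumbar puncture (under general anesthesia) to obtain CSF samples at the Screening and EOS Visits".
- **ECG, control.** Weeks 4, 16, 28 and 40 (protocol 8.3.3.2) and end of study (8.4.2).
- **ECG, IT arm.** Before surgery (8.3.1.1), before treatment at dosing visits (8.3.2.1, with no week restriction on this item), after injection (8.3.2.2: "12-lead ECG (performed within 4 hours of IT injection at Weeks 4, 16, 28, 40") and at end of study (8.4.1). The pre-surgery ECG can be waived: "The assessments indicated do not need to be repeated if completed as part of Screening assessments within 7 days prior to surgery".

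Values and changes from baseline, as distinct from abnormality flags, are summarised by visit and treatment group in both SAP sections.

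**The concern.** The chance that a patient is ever flagged rises with the number of times he is examined. If one arm is examined more often, its ever-flagged proportion is higher in expectation even when the risk at each examination is the same.

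The no-IT arm is the only randomised comparison for the safety of the regimen. A reader who sets the two percentages side by side could take a difference produced by the schedule for an effect of the drug, the device or the procedure. A reader who knows about the schedule could equally discount a real difference.

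Two of the 14 IT-arm CSF samples, at surgery and before the Week 4 dose, precede the first dose under the planned schedule. A finding there still counts as post-baseline for the IT arm.

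**Working it through.** The documents give no figure for this point, so there is nothing to reproduce. The check counts scheduled looks and then computes the expected ever-flagged proportion with no treatment effect.

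**1. Post-baseline looks per patient** (protocol 7.11.10, 8.3, 8.4; 12 injections)

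| Assessment | IT arm | Control |
|---|---|---|
| CSF | 1 surgery + 12 pre-dose + 1 end of study = 14 | 1 |
| ECG, pre-treatment ECG quarterly | 1 + 4 + 4 + 1 = 10 (9 if pre-surgery waived) | 4 + 1 = 5 |
| ECG, pre-treatment ECG at every dose | 1 + 12 + 4 + 1 = 18 (17 if pre-surgery waived) | 5 |
| Blood and urine | 4 + 1 = 5, or 6 with pre-surgery | 4 + 1 = 5 |

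The four terms in the ECG rows are pre-surgery, pre-treatment, post-injection and end of study. Both readings are carried because 8.3.2.1 limits neighbouring items to certain weeks but not the ECG. Appendix 1 has a footnote for assessments done only at Weeks 4, 16, 28 and 40, but its ECG row was not readable in the available text. It should be checked there.

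**2. Formula.** Let p be the probability of a flag at one look, the same in both arms, and k the number of looks.

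- Independent looks: P(ever) = 1 - (1 - p)^k.
- Within-patient correlation rho (beta-binomial): a = p(1 - rho)/rho, b = (1 - p)(1 - rho)/rho, and P(ever) = 1 - B(a, b + k)/B(a, b), where B is the beta function.

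Both p and rho are assumptions.

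**3. Independent looks** (% of patients ever flagged)

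| p | CSF, 14 vs 1 | ECG, 10 vs 5 | ECG, 18 vs 5 |
|---|---|---|---|
| 1% | 13.1 vs 1.0 | 9.6 vs 4.9 | 16.5 vs 4.9 |
| 2% | 24.6 vs 2.0 | 18.3 vs 9.6 | 30.5 vs 9.6 |
| 5% | 51.2 vs 5.0 | 40.1 vs 22.6 | 60.3 vs 22.6 |
| 10% | 77.1 vs 10.0 | 65.1 vs 41.0 | 85.0 vs 41.0 |

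For example, CSF at 5% is 1 - 0.95^14 = 0.512 against 1 - 0.95 = 0.05.

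**4. With correlation, p = 5%**

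| rho | CSF, 14 vs 1 | ECG, 10 vs 5 | ECG, 18 vs 5 |
|---|---|---|---|
| 0.2 | 27.8 vs 5.0 | 23.9 vs 16.5 | 30.7 vs 16.5 |
| 0.5 | 15.2 vs 5.0 | 13.8 vs 11.0 | 16.2 vs 11.0 |
| 0.8 | 8.3 vs 5.0 | 7.9 vs 7.1 | 8.6 vs 7.1 |

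Waiving the pre-surgery ECG changes little: at 5% and independence, 9 and 17 looks give 37.0% and 58.2%.

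**5. Blood and urine.** At 5% and independence, 6 against 5 looks gives 26.5% against 22.6%. Without the pre-surgery test, the counts are equal.

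**6. Shared visits only.** ECG becomes 5 against 5 and CSF 1 against 1. The expected no-effect difference is then zero for any p and rho, if visits are missed equally in the two arms.

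**The case against.** The strongest reply is that the rest of the safety plan already guards against this.

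- Values and changes are summarised by visit and arm. Shifts from normal or non-significant to clinically significant laboratory values are listed with the values over time. Clinically significant laboratory and ECG findings are also recorded as adverse events (protocol 7.14.1.1).
- All safety analysis is descriptive, with no testing (SAP 6.8).
- Repeated ECGs in a child with a chronic disease that affects the heart are unlikely to be independent. With about 16 controls, one patient is 1/16 = 6.25 percentage points, so the ECG gaps at correlation 0.5 or 0.8 amount to less than one control patient.
- Table layouts are in separate shells (SAP 9.1).

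Much of this stands. A reader might infer that a real safety signal could not be told apart from the additional looks. The documents do not support that, because the by-visit values, listings and adverse events allow a closer look. A reader might also infer inflated type I error, but no test is planned. Nor does the missing baseline condition for ECG create the imbalance, since it applies to both arms; it is a separate weakness of the same table.

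What the reply does not meet is the table itself. The by-visit summaries cover values, not abnormality or clinical-significance flags, and descriptive status does not remove the bias from a percentage shown by arm. The SAP 6.8.2 wording on dose does not help either, because the pivotal study has a single IT dose. SAP 6.8.4 already separates vital signs taken around injections from those taken in all patients; ECG and CSF flags get no such separation.

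**Conclusion.** The point holds for CSF and, less strongly, for ECG. With equal risk per look, the any-post-baseline proportions are expected to be higher in the IT arm. This is a statement about expectation; it does not say that the observed arms must differ in one small trial.

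- **CSF is the main problem.** The 14 to 1 ratio is clear from the protocol. At an assumed 5% per look, a gap remains across the correlations tried, from 51% against 5% down to 8% against 5%.
- **ECG is less certain.** The IT count is 9-10 or 17-18 depending on how protocol 8.3.2.1 is read. The gap may be small if abnormalities persist within a patient. The figure of 60% against 23% is the result for 18 independent looks and should not be read as a forecast.
- **Blood and urine tests are nearly balanced** (5-6 against 5). It would be wrong to extend the criticism to them, except that a patient-level table pooling them with CSF would inherit the CSF imbalance.

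The consequence is a between-arm difference that can be misread.

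**What to change.** In SAP 6.8.2 and 6.8.3 and the table shells:

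1. Base between-arm proportions on shared visits: for ECG, one pre-dose reading at each of Weeks 4, 16, 28 and 40 plus Week 52; for CSF, Week 52 only.
2. Count ECG abnormalities that are new or worse than at Screening.
3. Report surgery and interim pre-dose CSF, and pre-surgery and post-injection ECG, for the IT arm alone, with the number of assessments per patient. If pre-treatment ECGs are done at other dosing visits, put them here too.
4. Keep CSF separate from blood and urine in the clinical-significance table.
5. Reconcile the grouping by dose and overall in SAP 6.8.2 with protocol 10.7.3 ("post-baseline laboratory result will be presented by treatment group").

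No new data are needed and no safety information is dropped. The cost is SAP wording, revised shells and one additional IT-only table.

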1 INTRODUCTION

1.1 Mucopolysaccharidosis II (Hunter syndrome)

Mucopolysaccharidosis II (MPS II) is a rare, X-linked, inherited disease that affects males nearly exclusively. Its estimated incidence is 1 in approximately 162,000 live births.^{1,2} Though typically appearing normal at birth, all MPS II patients suffer from a progressive, serious, life-limiting disease.^{3,4}

The disease is caused by the absence of, or deficiency in, the activity of the lysosomal enzyme, iduronate-2-sulfatase which acts to cleave O-linked sulfate moieties from the glycosaminoglycan (GAG) molecules dermatan sulfate (DS) and heparan sulfate (HS).⁵ Insufficient activity of iduronate-2-sulfatase leads to progressive accumulation of GAG in nearly all organs and body tissues.

The central underlying pathophysiological process leading to the clinical manifestations of MPS II is the chronic accumulation of dermatan sulfate and heparan sulfate inside cellular lysosomes, resulting in cellular engorgement, organomegaly, tissue destruction, and organ system dysfunction. Accumulation of GAG affects nearly all cell types, tissues, and organs of the body including the respiratory tract, heart, liver, spleen, leptomeninges, bones, joints, oropharynx, head, neck, and central nervous system (CNS).⁶ Clinical manifestations include severe airway obstruction, skeletal deformities, cardiomyopathy and, in most patients, neurological decline.⁷ Death may occur in the first or second decade of life. Patients with attenuated disease may survive into adulthood, with airway obstruction and cardiac causes often contributing to death.⁴

Phenotypic expression of the disease spans a wide spectrum of clinical severity. However, two extremes at either end of the continuum of MPS II have been identified based on cognitive status.^{4,8} The first is broadly characterized as an “attenuated” or milder form in which intellectual and neurodevelopment faculties are largely intact, although somatic pathology is present. The term “severe” has been adopted to describe a second broad phenotype of MPS II patients who suffer from neurodevelopmental impairment in addition to somatic manifestations of the disease. It has been estimated that approximately three-quarters of MPS II patients will develop CNS involvement and be characterized as “severe.”⁸ Despite these characterizations, patients with predominantly somatic involvement may nevertheless have a life-limiting disease course.

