10.7.4 Electrocardiogram Evaluations

The 12-lead ECG parameters (heart rate [bpm], PR interval [msec], RR interval [msec], QRS interval [msec], QT interval [msec] and QTc [msec] interval) will be summarized in terms of absolute value and change from baseline. The corrected QT interval (QTc) will be calculated using Bazett's formula as QT divided by the square root of RR interval. The number and percentage of patients with ECG abnormalities by treatment group will be presented.

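### The ECG abnormality table does not separate new findings from those already present at Screening, which dilutes the comparison between arms

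*SAP*

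**What the plan says.** **ECG.** SAP 6.8.3 states: "The number and percentage of patients with ECG abnormalities post baseline will be presented by treatment group". Protocol 10.7.4 is looser and does not restrict the count to post-baseline recordings: "The number and percentage of patients with ECG abnormalities by treatment group will be presented". Neither mentions the Screening result, and 6.8.3 does not define an abnormality. Heart rate and the PR, QRS, QT and QTc intervals are summarised as values and changes from baseline by visit and arm. SAP 6.1 sets baseline at Screening. SAP 8.9 rules out by-patient listings that the text does not name, and no ECG listing is named.

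**Laboratory.** SAP 6.8.2 classifies each patient by whether he had "a Clinically Significant (CS) value at any time during the study post baseline", again whatever his baseline. The same paragraph goes further than the ECG section. It takes "Patients with a Normal or non-CS value for a particular laboratory parameter at baseline who experience a change to CS" and says that they "will be identified and listed separately along with the corresponding laboratory values over time". Protocol 10.7.3 plans only the unconditioned count: "The number and percentage of patients with any clinically significant post-baseline laboratory result will be presented by treatment group".

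**Adverse events.** Protocol 7.14.1.1 makes clinically significant ECG and laboratory abnormalities, and worsening of existing conditions, adverse events. SAP 6.8.1 defines treatment-emergent events by onset date and tabulates them by system organ class, preferred term and arm.

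**The concern.** Protocol 1.1 gives a reason to expect some abnormal ECGs before treatment: "Clinical manifestations include severe airway obstruction, skeletal deformities, cardiomyopathy". Protocol 7.11.6 has the reader assess rhythm and atrial or ventricular hypertrophy as well as intervals. A boy with hypertrophy at Screening and at Week 52 enters the planned numerator exactly as a boy who develops it on study.

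ECG results are part of the stated safety objective (Protocol 2.3), and safety is descriptive without testing (SAP 6.8), so readers will compare the printed percentages directly. If persisting abnormalities make up much of both percentages, a real excess in the IT arm looks small. With only 16 controls, randomisation cannot be relied on to balance Screening abnormalities.

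**Working it through.** The plan states no figure on this point, so there is none to reproduce.

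**Inputs from the documents.** 32 IT and 16 control boys (SAP 4.1).

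**Assumed inputs.** New-onset abnormality among boys normal at Screening: 15% IT, 5% control (ratio 3.0, difference 10 points). Proportion abnormal at Screening, p: 5% to 50%, the same true rate in both arms, all persisting.

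**Step 1: what the planned table shows on average.** Percentage = p + (1 − p) × new-onset rate. At p = 20%: IT 0.20 + 0.80 × 0.15 = 32.0%; control 0.20 + 0.80 × 0.05 = 24.0%. The difference is always (1 − p) × 10 points.

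**Step 2: chance imbalance at Screening.** SD of the arm difference = √[p(1 − p)(1/32 + 1/16)]. At p = 20%: √(0.16 × 0.09375) = 12.2 points.

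**Step 3: how often control looks worse than IT.** For the planned table this is an exact binomial calculation. For the comparison limited to boys normal at Screening it is a simulation of one million trials.

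| p | Planned IT v control | Ratio | SD of Screening imbalance | Control worse, planned | Control worse, conditioned |
|---|---|---|---|---|---|
| 5% | 19.3% v 9.8% | 1.97 | 6.7 points | 14% | 11% |
| 10% | 23.5% v 14.5% | 1.62 | 9.2 points | 18% | 12% |
| 20% | 32.0% v 24.0% | 1.33 | 12.2 points | 24% | 13% |
| 35% | 44.8% v 38.3% | 1.17 | 14.6 points | 29% | 15% |
| 50% | 57.5% v 52.5% | 1.10 | 15.3 points | 33% | 16% |

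At p = 0 the two tables coincide and nothing is lost.

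**Step 4: a reversal in counts.** Suppose 8 of 32 IT boys and 8 of 16 controls are abnormal at Screening. New onset is 6/24 (25%) in IT and 0/8 in control. The planned table prints (8 + 6)/32 = 43.8% for IT and 8/16 = 50.0% for control.

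**Step 5: what other outputs recover.** Mean changes in PR or QRS may show a group shift in conduction, but do not identify boys with a new abnormality, and they do not describe hypertrophy or rhythm. Treatment-emergent adverse events separate new or worsened from stable findings, but only those judged clinically significant. New hypertrophy, rhythm or conduction findings below that threshold are not separated from old ones.

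**The case against.** The strongest reply is that the clinically important part is already counted by arm. A new or worsened significant ECG or laboratory finding is an adverse event and appears in the treatment-emergent tables; a stable Screening abnormality does not. This stands. A reader might infer from the ECG table that the trial could miss or reverse a cardiac safety signal altogether. The documents do not support that: what stays unseparated is new ECG abnormality not reported as an adverse event.

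A reader might also infer that new laboratory findings are lost in the same way. They are not. SAP 6.8.2 identifies and lists them by parameter with values over time, and only a count by arm is missing. Nor do the tables count every abnormal result. Both count patients, the laboratory one counts clinically significant values only, and an old abnormality enters only if it is still present after baseline.

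On size, cardiomyopathy in a general disease description is not a Screening ECG prevalence for this trial. Eligibility excludes significant comorbidity and unacceptable anaesthesia risk (Protocol 5.3), so prevalence may be low; at 5% the wrong-direction rates are 14% v 11%. Persistence of every Screening abnormality is also assumed. Reversal needs a chance imbalance; on average the direction is kept.

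IT boys also have more ECGs, before surgery and after injections (Protocol 8.3.1.1 and 8.3.2.2), which raises their any-time count. That is a separate bias in the opposite direction, so net hiding is not established. It does not reliably cancel the dilution either.

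Finally, the table shells are a separate document (SAP 9.1) and may contain a shift table. The SAP text does not require one.

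**Conclusion.** The point holds for the ECG table and is a worthwhile correction to a descriptive analysis; primary inference and sample size are unaffected. Dilution follows from the definition whenever Screening abnormalities persist. Under the assumed rates, a new-onset difference of 10 points shrinks to between 9.5 and 5 points, and the ratio of 3.0 to between 1.97 and 1.10. All prevalence, persistence and new-onset values are assumptions, so the actual size is unknown and is nil if no boy is abnormal at Screening. For laboratory values the gap is minor: a count by arm is missing from information the SAP already lists.

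**What to change.** In SAP 6.8.3:
- Keep the existing count.
- Add, by arm, the number and percentage with a post-baseline abnormal ECG among boys whose Screening ECG was normal.
- Add a shift table of Screening category by worst post-baseline category.
- Define what counts as an abnormality and which categories are used.

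In SAP 6.8.2, keep the all-patients table of clinically significant values. Add a count by arm of the boys already listed as changing to clinically significant, with those not clinically significant at baseline as denominator. The SAP groups the present table by dose ("The number and percentage of patients in each category will be presented by treatment dose and overall"), whereas Protocol 10.7.3 says treatment group; the new count should be by treatment group.

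The cost is two further descriptive tables from data already collected. Denominators shrink: at 50% Screening prevalence about 16 × 0.5 = 8 controls remain, and under the assumed 5% rate no control has a new event in (1 − 0.5 × 0.05)^16 = 67% of trials. The tables should therefore show counts with their denominators, and ratios should not be relied on.
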